**Table 6. Estimated Sample Requirements Per Subject**

	Approximate sample volume per collection (mL)	Number of collection timepoints	Approximate total volume collected (mL)
Clinical laboratory tests	16.5	11	181.5
QuantiFERON® Gold/IGRA	11	1	11
Anti-GM-CSF autoantibody	2	1	2
PK	4	5	20
ADA	4	3	12
Cytokine and chemokine panel	8.5	5	42.5
SP-D, SAA, and biomarkers	5	5	25
FSH (if necessary)	3.5	1	3.5
Virology labs (hepatitis B, hepatitis C, and HIV)	5	1	5
Total:			302.5

### 7.2.12. Pregnancy Testing

WCBP must have a urine beta human chorionic gonadotropin ( $\beta$ -hCG) pregnancy test at study visits indicated on the SOA ([Appendix 1](#)). Following a negative pregnancy test at Screening and verification of appropriate contraception as outlined in [Section 4.4.2.6](#) and [Section 6.3](#), a negative pregnancy test result will be required at Day 1 (Baseline) prior to the subject receiving study drug and at subsequent visits where pregnancy testing is specified. Additionally, if the site staff become aware of a participant having a missed menstrual cycle between visits, the participant should come to the site for a urine pregnancy test (as an unscheduled visit if necessary). The Investigator may perform additional pregnancy tests at their discretion or as required by local regulations.

Urine pregnancy tests (supplied by the central laboratory) will be performed at the site. A positive urine  $\beta$ -hCG test must be followed up with a serum  $\beta$ -hCG pregnancy test. A positive pregnancy test prior to randomization requires exclusion. A positive urine  $\beta$ -hCG test during the study after randomization requires immediate interruption of study drug until a serum  $\beta$ -hCG is

performed and found to be negative. The participant must be discontinued from the study and followed if pregnancy is confirmed by a positive serum  $\beta$ -hCG.

## 7.3. Adverse and Serious Events

### 7.3.1. Adverse Events

AE definitions and assignment of severity and causality are detailed in [Appendix 3](#).

Non-serious AE collection will be initiated after the subject has been randomized/enrolled and continue to be collected through the follow up phone call visit.

Any sign, symptom, or illness occurring prior to first dose of double-blind study drug will be captured in the medical history. TEAEs are defined as any AE reported after the first dose of study drug and continue to be collected through the follow up phone call visit. AE definitions and assignment of severity and causality are detailed in [Appendix 3](#).

AEs will be elicited from the subject (or, when appropriate, from a caregiver, delegate, or the subject's legally authorized representative) by the study site staff using a non-leading question such as "How are you feeling today?" or "Have you had any health concerns since your last visit?"

The Investigator and any designees are responsible for detecting, documenting, and reporting events that meet the definition of an AE or SAE and remain responsible for following up AEs that are serious, considered related to the study drug or the study, or that caused the subject to discontinue the study drug (see [Section 4.4.2](#)).

### 7.3.2. Reporting Serious Adverse Events

All SAEs, occurring after the signing of the ICF until 56 days after the last dose of study drug, and regardless of study drug relationship, must be reported within 24 hours of becoming aware of the event to appropriate Sponsor/CRO Drug Safety representatives. The Investigator or study site personnel will provide the initial notification by completing the SAE page in the eCRF (which will trigger an automatic SAE alert email to safety contacts), which must include the Investigator's assessment of the relationship of the event to study drug and must be signed by the Investigator. There may be situations in which minimal information is available. However, it is very important that the Investigator always makes an assessment of causality. The Investigator may change his/her assessment of the causality based on follow-up information and should amend the SAE report form accordingly. The causality assessment is one of the criteria used when determining regulatory reporting requirements. SAE definitions and assignment of severity and causality are detailed in [Appendix 3](#).

Sponsor/CRO Drug Safety will forward SAE queries directly to the Investigator via email or through electronic data capture (EDC), requesting additional information. It is the Investigator's responsibility to be diligent in providing this information to Sponsor/CRO as soon as it is available. SAEs will be followed until resolution, stabilization, or death.

If an event meets serious criteria and it is not possible to access the EDC, the SAE should be submitted by completing SAE form electronically using this email address:

[contact]. If email access is not available, the SAE may be reported via fax using the below regional numbers or by telephone hotline:

US [contact]

Safety [contact]

### **7.3.3. Pregnancy**

Although not considered an SAE (unless the event occurs with a serious outcome), pregnancy ([Section 4.4.2.6](#)) information on female subjects will be collected by the authorized safety designee.

If a female subject becomes pregnant during the study, study drug should be discontinued immediately. The Investigator must complete and submit a Pregnancy Report Form (or designated form) within 24 hours of awareness of the pregnancy. In addition, subjects who become pregnant will complete the EOS or ET evaluations according to the SOA ([Appendix 1](#)).

Female subjects who become pregnant will also be followed to determine the outcome of the pregnancy and the presence or absence of a congenital abnormality will be documented by completion of a Pregnancy Outcome Reporting Form (or designated form) and should be submitted to the Sponsor once the outcome is known.

Generally, follow-up will be no longer than 6 to 8 weeks following the estimated delivery date. Any premature termination of the pregnancy (spontaneous or intended) must also be reported.

If a female partner of a male subject becomes pregnant during the study, the female partner must complete the female partner ICF and the same reporting and follow-up guidelines for female subjects must be followed.

### **7.4. Pharmacokinetic Analysis**

Predose blood samples will be collected into appropriately labeled tubes for measurement of namilumab plasma concentrations as specified in the SOA ([Appendix 1](#)) from all subjects who receive at least 1 dose of namilumab. The actual date and time (24-hour clock time) of each sample will be recorded.

Instructions for the collection and handling of biological samples will be provided in the laboratory manual. All samples must be processed and shipped as indicated to maintain sample integrity. Any deviations from the processing steps and any actions taken must be documented and reported to the Sponsor.

A specific bioanalytical method (detailed in BA sample analysis plan) will be used to measure plasma concentrations of namilumab.

### **7.5. Immunogenicity Assessment**

Blood samples will be collected based on the SOA ([Appendix 1](#)) from all subjects who receive at least 1 dose of namilumab. A specific bioassay to determine development of ADA will be performed using a tier approach, i.e., Screening, confirmatory, and titer assessment. The impact of ADA on the PK of namilumab will be assessed.

## **8. SAMPLE SIZE AND DATA ANALYSES**

This section outlines the statistical analysis strategy and procedures for the study.

### **8.1. Determination of Sample Size**

The sample size for this study is not based on formal statistical calculations of study power. The planned sample size is considered sufficient to meet the primary objective.

### **8.2. Analysis Populations**

The following analysis populations will be included for this study:

#### **8.2.1. Intent-to-treat Population**

The Intent-to-Treat (ITT) Population will include all randomized/enrolled subjects.

#### **8.2.2. Modified Intent-to-treat Population**

The modified ITT (mITT) Population will include all randomized/enrolled subjects who receive any amount of study drug. For analysis of endpoints defined as changes from baseline, subjects must also have at least 1 Baseline or post-baseline assessment. The mITT will be analyzed according to the treatment assigned. All efficacy analyses will be performed using the mITT Population.

#### **8.2.3. Per-Protocol Population**

The Per-Protocol (PP) Population will include all subjects in the ITT Population who have no major protocol violations. The PP Population will be used for sensitivity analyses of the efficacy measurements.

#### **8.2.4. Safety Population**

The Safety Population (SP) will include all randomized/enrolled subjects who receive any amount of study drug. The SP will be analyzed according to the treatment received. This set will be used for safety analyses.

### **8.3. General Considerations**

All statistical analyses will be conducted using SAS, Version 9.3 or later. Demographic and Baseline characteristics will be summarized by treatment arm. For continuous measures, the mean and standard deviation (SD) will be summarized. Categorical variables will be described by the count and proportion in each category.

### **8.4. Handling of Missing Data**

Missing data will not be imputed for safety or efficacy assessment. The reasons of missing data, including lost to follow-up, SAEs/AEs, and any other causes, will be identified, and the percentage of these subjects will be summarized by treatment. Large proportions of missing data may introduce bias, particularly if they are imbalanced between treatment groups. Possible bias due to missing data will be explored with sensitivity analysis.

More details will be pre-specified in the statistical analysis plan (SAP).

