#### **4.4.2.3. Participant Discontinuation/Withdrawal of Consent**

Subjects may withdraw from the study at any time, for any reason, and may leave the study without specifying a reason at his/her own request. Additionally, subjects may request destruction of any samples taken and not tested, and the Investigator must document this in the site study records.

The Investigator should make all efforts to obtain information about possible underlying AEs leading to the decision to withdraw from study participation. Any AE or SAE information elicited must be documented in the subject's source documents and the eCRF. Refer to the SOA ([Appendix 1](#)) for data to be collected at the time of study discontinuation and follow-up and for any further evaluations that need to be completed.

Unless the subject who prematurely discontinues trial participation, specifically withdraws consent for any follow-up contact, all subjects will continue to be contacted at the same visit interval through the end of the study to obtain their health status. Investigators and site staff should encourage subjects to allow as much follow-up as possible and will need to clearly identify and document in writing as to which of the following options the subject has chosen.

- The subject has withdrawn from further treatment with study drug but will agree to continue with study visits and study assessments through the end of the Double-blind Treatment Period.
- The subject has withdrawn from further treatment with study drug, will not agree to continue with study visits and study assessments, but will agree to phone call assessments in accordance with the visit schedule.
- The subject is not willing to be contacted in accordance with the visit schedule but will allow the Investigator access to their medical records and EOS contact.

- The subject is not willing to allow any direct contact, access to medical records, or contact with care provider. In this case, public records may be used to confirm vital status at the end of the study.

For the purpose of this protocol, only subjects who are not willing to allow any direct contact, access to medical records, or contact with care provider will be deemed as subjects who have withdrawn consent.

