#### 4.4.2.5. Cardiac Changes

If a clinically significant finding is identified (including, but not limited to changes from baseline in QTcF after enrollment), the Investigator or qualified designee will determine if the subject can continue in the study and if any change in subject management is needed. This review of the ECG printed at the time of collection must be documented. Any new clinically relevant finding should be reported as an AE.

A subject who meets the following criterion based on the average of triplicate ECG readings will be withdrawn from the study.

- QTcF >500 msec OR uncorrected QT >600 msec.

For subjects with underlying bundle branch block, follow the discontinuation criteria listed in [Table 2](#).

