### **5.3.1.     Dose Modification**

Dose reductions will not be allowed. If a dose reduction is needed, the subject should be discontinued from study drug and all EOT assessments completed. See [Section 4.4.2.2](#) for missed doses.

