### **5.5.2. Corticosteroid Use and Taper Compliance**

Corticosteroids (OCS) will be self-administered by the subjects during the study. At each study visit, Investigators must review and document a subject's compliance with OCS use and taper during the corticosteroid tapering period and throughout the study until the subject completes their EOT/ET Visit. In order to verify corticosteroid dose on a daily basis, subjects will be required to complete an eDiary to document their steroid intake.

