Randomization and/or treatment assignment		X																
Administration of study drug		X	X		X		X		X		X		X	X	X			

Abbreviations: β-hCG = beta human chorionic gonadotropin, ADA = anti-drug antibodies, CT = computed tomography, ECG = electrocardiogram, ECHO = echocardiogram, EOS = End-of-Study, EOT = End-of-Treatment, ET = early termination, FAS = Fatigue Assessment Scale, FDG = fluorodeoxyglucose, FSH = follicle-stimulating hormone, FU = Follow-up Visit, GM-CSF autoAb = granulocyte macrophage colony-stimulating factor autoantibody, HbA1C = glycosylated hemoglobin, Hep = hepatitis, HIV = human immunodeficiency virus, hsCRP = high-sensitivity C-reactive protein, KSQ = King's Sarcoidosis Questionnaire, mGTI = modified glucocorticoid toxicity index,

NT-proBNP = N-terminal (NT)-proB-type natriuretic peptide, PET = positron emission tomography, PK = pharmacokinetic, PRO = patient-reported outcome, SAA = serum amyloid A, SGA = Subject Global Assessment, SP-D = serum surfactant protein D, TB = tuberculosis, WCBP = woman of childbearing potential.

- a. The Investigator will conduct weekly FU (via phone, telemed, or any site-approved remote method).
- b. Subjects who withdraw or are withdrawn from the study early will undergo all Week 34 ET/EOT Visit procedures whenever possible.
- c. The FU will be a phone call approximately 8 weeks (56 days) following the last dose of study drug.
- d. Collect medication history from the 6 months leading up to, and including, the time of the Screening Visit, including prescription medications, over-the-counter medications, and herbal supplements/vitamins.
- e. A full physical examination will be performed at Screening and the EOT/ET Visit; an abbreviated targeted physical examination will be performed at all other clinic Visits.
- f. Height will be measured at Screening only; weight will be measured at all indicated timepoints.
- g. Vital signs will be assessed at all timepoints specified above. On study drug administration days, vital signs will be assessed predose (within 15 minutes) and  $\pm 30$  minutes post-dose.
- h. Subjects will be monitored via ePatch for 10 consecutive days; one patch will be worn for 5 days, then the patch will be replaced by the subject, and the second patch will be worn for an additional 5 days.
- i. A single 12-lead standard ECG will be recorded at all timepoints specified above.

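### The protocol gives no single rule on which steroid and rhythm data are collected after study drug stops early, although both cumulative endpoints keep every dosed subject and allow no imputation

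*Combined protocol and SAP*

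**What the plan says.** **Endpoints and analysis.** Section 2.2 lists cumulative OCS use and cumulative arrhythmia burden as secondary endpoints. Its Week 34 note covers only mean-change endpoints, so neither cumulative endpoint has a stated window. The mITT population (Section 8.2.2) takes in every dosed subject; the added assessment condition applies only to change from baseline. Section 8.4 states: "Missing data will not be imputed for safety or efficacy assessment". It also promises a sensitivity analysis and further detail in the SAP.

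**Collection after an early stop.**
- Section 4.4.2.1: stopping drug is not in itself withdrawal from participation.
- Section 4.4.2.3: unless contact is refused, "all subjects will continue to be contacted at the same visit interval through the end of the study to obtain their health status". Under the first option the subject "will agree to continue with study visits and study assessments through the end of the Double-blind Treatment Period". Under the second the subject "will not agree to continue with study visits and study assessments, but will agree to phone call assessments in accordance with the visit schedule". The third option leaves records access and an end-of-study contact; the fourth leaves nothing.
- Section 4.4.2.2: after more than one missed dose, only safety follow-up is mentioned.
- Section 5.3.1: where a dose reduction would be needed, "the subject should be discontinued from study drug and all EOT assessments completed".
- Section 4.4.2.5, for the QT criterion: "A subject who meets the following criterion based on the average of triplicate ECG readings will be withdrawn from the study".
- Appendix 1, note b: "Subjects who withdraw or are withdrawn from the study early will undergo all Week 34 ET/EOT Visit procedures whenever possible".
- Section 5.5.2: steroid review runs "throughout the study until the subject completes their EOT/ET Visit".

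**Other sources of the same data.** Section 6.1, Section 3.1.3 and Appendix 1 notes c and l collect concomitant medication, with dose and dates, through the end-of-study call about 56 days after the last dose. The ePatch (Section 7.1.1.2) is placed at clinic visits from Screening through Week 30 and worn for 10 days. Appendix 1 shows none at the EOT/ET visit.

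**The concern.** A cumulative total is only as complete as its recording period. Two sites with identical subjects could follow different sections. One could keep the eDiary and patches going to Week 34; the other could complete an EOT visit when drug stops and then follow for safety only. Both subjects stay in the analysis. A total cut off early looks like low steroid use or few arrhythmias, and if early stopping differs between the Cohort A arms, the comparison is biased. The direction is unknown because the affected arm is unknown. If loss were equal in number and timing, the part driven by the planned schedule would cancel.

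An SAP can choose how to handle a gap but cannot create doses or rhythm recordings that nobody took. The stake is a misleading steroid-sparing or arrhythmia signal carried into the design of the next trial.

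**Working it through.** The plan states no figure to reproduce: Section 8.1 has no power calculation, and no early-stop rate is given. The check therefore sizes the gap under stated assumptions.

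**Inputs from the documents.** 10 subjects per arm (synopsis); 238 treatment days; Appendix 8 course of 25 mg/day by Week 4 and through Week 10, tapering to 10 mg/day by Week 22, then 10 mg/day or less; end-of-study call 56 days after the last dose.

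**Assumptions.** Start at 25 mg/day; linear taper; exactly 10 mg/day after Week 22; last study-drug dose at Week 10; 2 of 10 subjects in one arm affected and none in the other; OCS known up to the end-of-study call and not after it.

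**Planned course.** 25×28 + 25×42 + 17.5×84 + 10×84 = 700 + 1,050 + 1,470 + 840 = 4,060 mg, of which 1,750 mg falls by Week 10.

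**Gap after the call.** Week 10 plus 56 days is Week 18. The tapering dose is then 25 − 15×8/12 = 15 mg/day. Unrecorded: 12.5×28 + 10×84 = 350 + 840 = 1,190 mg, and 1,190/4,060 = 29%. A higher starting dose leaves the 1,190 mg unchanged, because all courses meet at 25 mg/day by Week 4.

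**Case A: the two subjects would have followed the taper.** True arm mean 4,060 mg. Summed as recorded, the error is −1,190×2/10 = −238 mg (−5.9%).

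**Case B: they stayed at 25 mg/day.** Own total 1,750 + 25×168 = 5,950 mg. True arm mean (8×4,060 + 2×5,950)/10 = 4,438 mg. Unrecorded 25×112 = 2,800 mg each, so the error is −560 mg (−12.6%). The recorded mean is 3,878 mg. Against a complete arm at 4,060 mg, a true excess of 378 mg appears as a saving of 182 mg.

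| Handling of the 2 subjects | Case A | Case B |
|---|---|---|
| Sum as recorded | −238 mg | −560 mg |
| Completers only | 0 | −378 mg |
| Hold last recorded dose to Week 34 | +98 mg | 0 |

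The +98 mg is (15×112 − 1,190)×2/10. No row is right in both cases; only recorded doses are. For 1 to 3 of 10 subjects, summing as recorded gives −119 to −357 mg (A) or −280 to −840 mg (B).

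**Outer bound.** With no OCS information at all after Week 10, the sums would err by (4,060 − 1,750)×2/10 = 462 mg (A) or 25×168×2/10 = 840 mg (B), both downward.

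**Rhythm.** Patches at Weeks 0, 2, 6, 10, 14, 18, 22, 26 and 30 give 9×10 = 90 scheduled days. A subject whose clinic visits end before the Week 10 patch contributes 30. Two such subjects of 10 lower a raw arm-mean count by 2/10×60/90 = 13% at an equal event rate; if visits end before the Week 22 patch (60 of 90 days), by 7%.

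**The case against.** The best reply is that steroid collection is fuller than Section 5.5.2 suggests. OCS is a concomitant medication, so its dose and dates are due up to the end-of-study call. The second option in Section 4.4.2.3 gives phone assessments on the visit schedule, and Appendix 1 marks steroid-dose recording at the phone visits and at Weeks 22, 26, 30 and 34. The eDiary sentence has no early cut-off. This stands, and it rules out a stronger reading that a reader might draw, namely that nothing is known about steroids once drug stops; the outer bound above is a worst case. It does not close the gap. For an early stopper the end-of-study call can precede Week 34, the stated purpose of continued contact is health status, and other sections point to an early EOT visit.

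Second, some of these sections concern stopping drug and others leaving the study, so not every difference is a contradiction. That is fair. What remains open is whether Section 5.3.1 brings the EOT visit forward, how far the safety follow-up in Section 4.4.2.2 extends, and what is collected after withdrawal from the study.

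Third, Section 8.4 does not say that truncated totals are summed. It warns about imbalanced missing data and defers detail to the SAP, for which no separate text was available here. So one cannot infer that the plan treats unrecorded days as zero. The window and the partial-data method are points to confirm, not faults.

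Fourth, the early-stop numbers are assumed, and Section 4.4.4 allows replacement. That is also true, but a replaced subject who was dosed stays in the mITT population.

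**Conclusion.** The point holds as a conflict about data collection. Sections 4.4.2.2, 4.4.2.3, 4.4.2.5, 5.3.1 and 5.5.2 and note b of Appendix 1 do not add up to one rule, and two secondary endpoints depend on the answer. For steroids the gap is partial: about 29% of the planned course for a subject whose last dose is at Week 10 and whose information ends at the call. In the assumed 2-versus-0 imbalance, summing as recorded shifts the arm mean by −238 to −560 mg. For rhythm there is no fallback, because phone contact cannot replace a patch placed in clinic. Withdrawal on the QT criterion is triggered by an ECG finding, so that loss may not be independent of rhythm, but the documents give no frequency and nothing more should be read into it.

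A reader might also infer a risk of a false efficacy claim. The documents do not support that: Section 8.5 plans no hypothesis testing and treats nominal p values as descriptive. The between-arm issue concerns Cohort A only. This is a modest-priority correction.

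**What to change.** **Protocol.** Reconcile the sections named above on data collection only, with no change to any dose, taper or stopping rule. State that early discontinuation of study drug does not end steroid-dose recording. It continues to Week 34, by eDiary or by a dose question at the contacts already planned in Section 4.4.2.3, for every subject who accepts contact. State that the ePatch continues for subjects who still attend visits, and say what is collected from those withdrawn from the study.

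**SAP (confirm or add).** Define cumulative OCS from Day 1 to Week 34 using all recorded doses, including those from concomitant-medication records. Analyse arrhythmia as a rate per analysable recorded time; whether the device export gives that time needs checking. Give one sensitivity analysis for days still unrecorded, such as the last recorded dose held to Week 34, written openly as an exception to Section 8.4. Averaging each visit interval over subjects with records should not be presented as free of imputation: it gives the same arm mean as filling missing intervals with that arm's interval mean. Use the same definitions in Cohort B, descriptively.

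**Cost.** One protocol clarification with IRB approval, some SAP wording, and a small burden on subjects who stop drug. Phone-only subjects still give no rhythm data, and a rate does not remove bias if stopping is related to rhythm.
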